## 11.2 SERIOUS ADVERSE EVENTS

Serious adverse event collection begins after the patient or surrogate has signed informed consent and has received study drug or undergone study procedures. If a patient experiences a serious adverse event after consent, but prior to receiving study drug, the event will NOT be collected unless the investigator feels the event may have been caused by a protocol procedure.

Study site personnel must alert the CCC of any **serious and study drug or study procedure related** adverse event within 24 hours of investigator awareness of the event. Alerts issued via telephone are to be immediately followed with official notification on the adverse event case report form. See Appendix C for reporting timelines for serious, unexpected, study related events (SAEs) and serious, unexpected suspected adverse reactions (SUSARs)

As per the FDA and NIH definitions, a serious adverse event is any adverse event that results in one of the following outcomes:

- Deaths

- A life-threatening experience (that is, immediate risk of dying)
- Prolonged inpatient hospitalization or rehospitalization

As per <http://www.fda.gov/Safety/MedWatch/HowToReport/ucm053087.htm>: Report if admission to the hospital or prolongation of hospitalization was a result of the adverse event. Emergency room visits that do not result in admission to the hospital should be evaluated for one of the other serious outcomes (e.g., life-threatening; required intervention to prevent permanent impairment or damage; other serious medically important event).

- Persistent or significant disability/incapacity

As per <http://www.fda.gov/Safety/MedWatch/HowToReport/ucm053087.htm>: Report if the adverse event resulted in a substantial disruption of a person's ability to conduct normal life functions, i.e., the adverse event resulted in a significant, persistent or permanent change, impairment, damage or disruption in the patient's body function/structure, physical activities and/or quality of life.

Important medical events that may not result in death, be life-threatening, or require hospitalization may be considered serious adverse events when, based upon appropriate medical judgment, they may jeopardize the patient and may require medical or surgical intervention to prevent one of the outcomes listed in this definition.

Serious adverse events will be collected during the first **7 study days** or until ICU discharge, whichever occurs first, regardless of the investigator's opinion of causation. Thereafter, serious adverse events are not required to be reported unless the investigator feels the events were related to either study drug or a protocol procedure.

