## 1.2 DEFINITIONS

**Adverse Event:** Any untoward medical occurrence associated with the use of a drug or a study procedure, whether or not considered drug related.

**Adverse reaction:** An adverse reaction means any adverse event caused by a drug. An adverse reaction are a subset of all suspected adverse reactions where there is a reason to conclude that the drug caused the event.

**Assisted breathing:** Any level of ventilatory support at pressures higher than the unassisted breathing thresholds. Completing 48 hours of UAB is defined as the date (calendar day) that the subject reaches exactly 48 hours of UAB. Example: if subject meets UAB at 1900 on 6/1/15 and does not return to assisted breathing, then the date of completing 48 hours of UAB would be 6/3/15.

**Controlled Ventilation:** Any mode with a backup rate that allows clinicians to either set tidal volume to a target or adjust pressures to target a tidal volume. Examples include volume assist control, pressure assist control, pressure regulated volume control.

**Extubation:** Removal of an orotracheal, nasotracheal tube, or unassisted breathing with a tracheostomy

**Home:** Level of residence or health care facility where the patient was residing prior to hospital admission.

**Intention to Treat (ITT):** All eligible and consented patients who undergo randomization will be included in the ITT cohort for the purposes of analyzing the primary and secondary study outcomes.

**Invasive Mechanical Ventilation:** Assisted ventilation delivered by a nasotracheal, orotracheal, or tracheostomy tube

**Legal Representative:** An individual, judicial, or other body authorized under applicable law to consent on behalf of a prospective patient to the patient's participation in the clinical study.

**Mortality prior to discharge home before day 90:** This primary outcome includes deaths from all causes following randomization in any health care facility prior to discharge home until study day 90. Study subjects still in a health care facility at study day 91 are considered alive for this endpoint.

**Funding:** National Institutes of Health (National Heart Lung and Blood Institute)

**Sponsor:** The Clinical Coordinating Center at Massachusetts General Hospital

**Study Day:** The day of randomization is study day zero. The next day is study day one etc.

**Study Drug:** Randomly assigned cisatracurium

**Study hospital:** Defined as the hospital where the patient was randomized and enrolled.

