# 11 ADVERSE EVENTS

## 11.1 SAFETY MONITORING

Assuring patient safety is an essential component of this protocol. Each participating investigator has primary responsibility for the safety of the individual participants under his or her care. The Investigators will determine daily if any adverse events occur during the period from enrollment through **study day 7** (five days after infusion of study drug) or ICU discharge, whichever occurs first.

The following adverse events will be collected in the adverse event case report forms:

- Serious adverse events
- Nonserious adverse events that are considered by the investigator to be related to study drug or study procedures or of uncertain relationship (Appendix C2)
- Adverse events that lead to permanent discontinuation of the study drug infusion
- Hypersensitivity reactions to cisatracurium, severe prolonged bradycardia (heart rate < 50 for > 30 minutes), and paralysis recall
- Hypotension or pneumothorax, considered by the investigator to be related to high PEEP, or of uncertain relationship.

A clinical trial adverse event is any untoward medical event associated with the use of a drug or study procedure in humans, whether or not it is considered related to a drug or study procedure.

After randomization, adverse events related to protocol procedures or occurring after the patient receives the first dose of study drug must be evaluated by the investigator. If the adverse event is judged to be reportable, as outlined above, then the investigator will report to the CCC their assessment of the potential relatedness of each adverse event to protocol procedure or study drug via electronic data entry. Investigators will assess if there is a reasonable possibility that the study drug or procedure caused the event, based on the criteria outlined in Appendix C2. Investigators will also consider if the event is unanticipated or unexplained given the patient's clinical course, previous medical conditions, and concomitant medications.

If a patient's treatment is discontinued as a result of an adverse event, study site personnel must report the circumstances and data leading to discontinuation of treatment in the adverse event case report forms.

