## C ADVERSE EVENT REPORTING AND UNANTICIPATED PROBLEMS

As noted in section 11.2, investigators will report all adverse events that are serious and study drug or study procedure related to the CCC within 24 hours. The CCC will then notify the NHLBI and cIRB.

The Medical Monitor at the CCC will work collaboratively with the reporting investigator to determine if a serious adverse event has a reasonable possibility of having been caused by the study drug or procedure, as outlined in 21 CFR 312.32(a)(1)I, and below (Appendix C2). The Medical Monitor will also determine if the event is unexpected. An adverse is considered “unexpected” if it is not listed in the investigator brochure or the study protocol (21 CFR 312.32(a)). For this study, the cisatracurium (Nimbex®) package insert and the ACURASYS Study serve as the investigator brochure. If a determination is made that a serious adverse event has a reasonable possibility of having been caused by the drug, it will be classified as a suspected adverse reaction. If the suspected adverse reaction is unexpected, it will be classified as a serious unexpected suspected adverse reaction (SUSAR).

The CCC will report all unexpected and study related deaths, SAEs, and SUSARs to the DSMB, NHLBI, and cIRB within 7 days after receipt of the report from a clinical site. A written report will be sent to the NHLBI, DSMB and the cIRB within 15 calendar days. All unexpected and study related deaths and life threatening SUSARS will be reported to the FDA within 7 days; all other SUSARS will be reported to the FDA within 15 days. The DSMB will also review all adverse events and clinical outcomes during scheduled interim analyses, including frequency of additional neuromuscular blockade use in both study groups, for the first 48 hours. If the DSMB determines that the overall rate of adverse events is higher in the cisatracurium group than the control group the cIRB and the FDA will be notified within 15 days of this determination (via an IND safety report (21 CFR 312.32(c)(1)(i)(A))). The CCC will distribute the written summary of the DSMB’s periodic review of adverse events to the cIRB in accordance with NIH guidelines (<http://grants.nih.gov/grants/guide/notice-files/not99-107.html>).

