### 2.5 Adverse Events

Adverse events will be analyzed using weighted Poisson regression with non-serious events weighted by one and serious events weighted by two. Events rather than patients will be the unit of analysis. Adverse events will be grouped and analyzed separately by MeDRA system organ classes, and MedDRA preferred term.

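### Protocol 11.1 and 11.2 give conflicting rules for collecting serious adverse events, and two of them depend on study drug, which control patients never receive

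*Protocol*

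**What the plan says.** **Sentences keyed to study drug**

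- Protocol 11.2, second sentence, on serious events: "after consent, but prior to receiving study drug, the event will NOT be collected unless the investigator feels the event may have been caused". The cause meant is a protocol procedure, and no arm is named.
- Protocol 11.1, for the post-randomization period: "adverse events related to protocol procedures or occurring after the patient receives the first dose of study drug must be evaluated by the investigator". There is no branch for an unrelated event in a patient who gets no study drug.
- Protocol 1.2 defines study drug as "Randomly assigned cisatracurium". The trial is unblinded and has no placebo, so controls never receive study drug in this sense, even if they are given open-label cisatracurium.

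**Sentences that apply to both arms**

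- Protocol 11.2, first sentence: collection starts once a consented patient "has received study drug or undergone study procedures".
- Protocol 11.1: investigators check daily for adverse events from enrollment to study day 7 or ICU discharge. The list of events to record begins with serious adverse events, without condition.
- Protocol 11.2, closing paragraph: serious events in the first seven study days, or up to ICU discharge, are collected "regardless of the investigator's opinion of causation".

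**Where the data go**

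- SAP 2.5 uses a weighted Poisson regression in which serious events count double: "Events rather than patients will be the unit of analysis". It states no time origin.
- Appendix C: "If the DSMB determines that the overall rate of adverse events is higher in the cisatracurium group than the control group", the central IRB and the FDA are to be notified within 15 days.

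**The concern.** A between-arm comparison of event counts is fair only if both arms are observed under the same rule. Here two operative sentences depend on something that only one arm receives. Read literally, they admit every serious event after the first dose in the cisatracurium arm, but in the control arm only those that the investigator thinks a procedure may have caused.

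Three features raise the stakes. Safety is part of the primary objective (Protocol 3.8), and under-reporting of safety outcomes is one of the stated reasons for repeating the earlier French trial (Protocol 3.6). The exception rests on the judgement of an unblinded investigator; Protocol 5.1.1 accepts the open-label design because mortality is objective, and that argument does not extend to adverse events. Appendix C attaches a regulatory consequence to a higher overall rate on cisatracurium and gives no numerical threshold, so an imbalance in recording could contribute to it, or could mask a true excess in controls.

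**Working it through.** **1. A test case.** Take a serious ventricular tachycardia on study day 3, judged unrelated to any study procedure. Appendix C3 says that such an arrhythmia is not an exempt outcome.

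| Rule | Cisatracurium patient, after first dose | Control patient |
|---|---|---|
| 11.2, first sentence | within collection | within collection, through study procedures |
| 11.2, second sentence | does not apply | not collected |
| 11.1, list of events to record | collected | collected |
| 11.1, evaluation sentence | must be evaluated | no requirement |
| 11.2, closing paragraph | collected | collected |

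For the cisatracurium patient the rules agree. For the control patient they do not, and nothing says which prevails.

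**2. Possible size if control events are lost.** The plan gives no adverse event rate or safety power calculation, so there is no stated figure to reproduce. The inputs are:

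- n = 1408/2 = 704 per arm. The maximum of 1408 is in the protocol; equal allocation is assumed, because no ratio is stated.
- λ = collectable serious events per patient, equal in both arms: assumed 0.05, 0.10 or 0.20.
- m = share of control serious events not collected: assumed 10%, 25% or 50%.

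Expected recorded counts are a = nλ (cisatracurium) and c = nλ(1 − m) (control). The recorded ratio is 1/(1 − m). With z = ln[1/(1 − m)] / √(1/a + 1/c), the chance of a two-sided p<0.05 is 1 − Φ(1.96 − z) + Φ(−1.96 − z).

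Worked case, λ = 0.10 and m = 25%: a = 70.4 and c = 52.8; ln(1.333) = 0.288; √(1/70.4 + 1/52.8) = 0.182; z = 1.58; chance = 0.35.

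| Share of control events lost | Recorded ratio | λ = 0.05 | λ = 0.10 | λ = 0.20 |
|---|---|---|---|---|
| 10% | 1.11 | 0.07 | 0.09 | 0.14 |
| 25% | 1.33 | 0.20 | 0.35 | 0.61 |
| 50% | 2.0 | 0.66 | 0.92 | >0.99 |

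The last three columns give the chance of a spurious p<0.05. The test is unweighted and covers serious events only. SAP 2.5 plans a weighted analysis that also includes non-serious events, so these are not the error rates of the planned test.

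**3. Other readings.**

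- If sites follow the closing paragraph of 11.2, m = 0 and the ratio is 1.
- If the second sentence of 11.2 is applied only to the active arm's wait for the first dose (up to four hours, Protocol 4.4), that arm loses up to 4 of 7 × 24 = 168 hours, or 2.4%. With a constant hazard the ratio is 1 − 0.024 = 0.98, a slight bias in favour of cisatracurium.

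**The case against.** A reader might infer that adverse events are collected only from the first dose, so that control events are in fact under-collected and the safety comparison is biased. The documents do not support that.

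- The first sentence of 11.2 admits controls through study procedures, and they all undergo some: the PEEP protocol and low tidal volume ventilation (5.3.3) and research specimens (6.3.3).
- The 11.1 window, its list of recordable events and the closing paragraph of 11.2 are all arm-neutral.
- The disputed sentence can fairly be read as covering only the wait between consent and treatment. Stretching it over a control patient's whole follow-up cancels its neighbours.
- The 11.1 evaluation sentence leads into the assessment of relatedness; what is recorded is set by the list above it.
- Appendix C4 contains a decision tree on reportability. It is a figure and is not shown in the text available here, so it may settle the matter for sites.
- Death, organ failure, rescue procedures, pneumothorax, supraventricular arrhythmia and paralysis recall are recorded in both arms as outcomes. Appendix C3 exempts many common ICU events in both arms.
- Appendix C notification follows a determination by the DSMB, not an automatic test.

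Most of this stands. It makes the bias conditional and narrows the events exposed to it. It does not remove the contradiction: the sentence names no arm, it is emphatic, and taken literally it conflicts with the text on either side. The waiting-period reading still leaves collection dependent on arm, though only slightly.

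**Conclusion.** The concern holds as an inconsistency that has to be resolved, not as a demonstrated bias. Protocol 11.1 and 11.2 give incompatible instructions for a control patient whose serious event is judged unrelated to procedures. The data collected under them feed both the SAP 2.5 comparison and the Appendix C rate comparison.

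Size and direction depend on what sites do. The ratio is 1 if all serious events are collected, about 0.98 if only the active arm's pre-dose gap is excluded, and 1.33 or 2.0 if 25% or 50% of control serious events are dropped. The chances of 0.35 and 0.92 attached to the last two rest on assumed inputs (704 per arm, 0.10 events per patient, equal true rates, an unweighted test). The documents supply neither an event rate nor the share of control events that would be lost. The point merits action before data are collected because events never recorded in controls are hard to recover afterwards.

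**What to change.** Reconcile Protocol 11.1 and 11.2 to a single rule: in both arms, collect serious adverse events from randomization through study day 7 or ICU discharge, whichever is earlier, whatever the judged relationship. Delete the two conditions that refer to receipt of study drug (the second sentence of 11.2 and the first-dose trigger in 11.1). State the same time origin in SAP 2.5, and check that the Appendix C4 decision tree agrees.

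Do not take hypersensitivity or other drug-related events out of the Appendix C comparison to make the arms look more alike. Those are genuine potential harms of the drug, and controls may receive open-label cisatracurium (5.1.1, 5.2.1), so hypersensitivity is not confined to one arm.

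The cost is revised wording in the protocol, SAP and site guidance, and a modest increase in recorded control events, limited by the Appendix C3 exemptions. The design and sample size do not change.

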## 12 APPENDICES

### A1 S/F RATIO INCLUSION CRITERIA

Table 2 displays an equivalence table that determines the estimated P/F ratio from the FiO2 and SpO2. This data was generated by investigators at the University of Utah, on a cohort of critically ill patients with pneumonia.[72-78].

Table 2: Imputed PaO2/FiO2 for combination of SpO2 (rows) and FiO2 (columns)

SPO2	FiO2														
	0.3	0.35	0.4	0.45	0.5	0.55	0.6	0.65	0.7	0.75	0.8	0.85	0.9	0.95	1
80%	148	127	111	98	89	81	74	68	63	59	55	52	49	47	44
81%	151	129	113	101	91	82	76	70	65	60	57	53	50	48	45
82%	155	132	116	103	93	84	77	71	66	62	58	55	52	49	46
83%	158	136	119	106	95	86	79	73	68	63	59	56	53	50	47
84%	162	139	122	108	97	89	81	75	70	65	61	57	54	51	49
85%	167	143	125	111	100	91	83	77	71	67	63	59	56	53	50
86%	171	147	129	114	103	94	86	79	73	69	64	61	57	54	51
87%	177	151	132	118	106	96	88	81	76	71	66	62	59	56	53
88%	182	156	137	121	109	99	91	84	78	73	68	64	61	58	55
89%	189	162	141	126	113	103	94	87	81	75	71	67	63	60	57
90%	196	168	147	130	117	107	98	90	84	78	73	69	65	62	59
91%	203	174	153	136	122	111	102	94	87	81	76	72	68	64	61
92%	213	182	159	142	128	116	106	98	91	85	80	75	71	67	64
93%	223	191	168	149	134	122	112	103	96	89	84	79	74	71	67
94%	236	202	177	157	142	129	118	109	101	94	89	83	79	75	71
95%	252	216	189	168	151	138	126	116	108	101	95	89	84	80	76
96%	273	234	205	182	164	149	136	126	117	109	102	96	91	86	82

For altitude adjustment, we would recommend the practice from ARDS Network studies of multiplying the qualification threshold P/F by the ratio of average ambient to sea level barometric pressure (for Utah, it is  $0.86 \times 150 = 129$ ; for Denver it is  $0.84 \times 150 = 126$ ).

Additional requirements for the use of the S/F ratio include:

1. SpO2 between 80-96%
2. SpO2 should be measured at least 10 minutes after any change in FiO2.
3. PEEP  $\geq$  8 cm H2O
4. An adequate pulse oximeter waveform tracing

## A2 EXCLUSION DEFINITIONS

### Child-Pugh Score [79]

Premorbid values within 1 year of enrollment should be used.

Points	Class
5-6	A
7-9	B
≥ 10	C

Measurement	Numerical Score for Increasing Abnormality		
	1	2	3
Ascites	None	Present	Tense
Encephalopathy	None	Grade I or II	Grade III or IV
Bilirubin (mg/dl)	< 2	2-3	> 3
Albumin (g/L)	> 35	28-35	< 28
Prothrombin time (sec. prolonged)	1-4	4-10	> 10

NOTE: If using INR instead of Prothrombin time for Child-Pugh calculation, points for INR are as follows:

<1.7 = 1point

1.7-2.3 = 2points

>2.3 = 3points

### Neuromuscular Disease That May Potentiate Neuromuscular Blockade or Impair Spontaneous Ventilation

1. Amyotrophic lateral sclerosis
2. Guillain-Barré Syndrome
3. Myasthenia gravis
4. Upper spinal cord injury at level C5 or above

## B TIME-EVENTS SCHEDULE

Measurement/Event	Day 0	1	2	3	4	5	6	7	14	21	28	90
Demographics, History and Physical	X											
Etiology of ARDS	X											
APACHE III	X											
HCG (females)	X											
Alcohol Use/Smoking History	X											
CXR (number of quadrants)	X											
Study NMB Administration	X	X	X									
Baseline LTO	X											
Non-protocol NMB administration	X	X	X	X	X							
Level of Sedation	X	X	X	X	X	X	X	X				
Sedation Interruption (y/n)	X	X	X	X	X	X	X	X				
Gross motor assessment				X								
ICU Mobility Scale		X	X	X	X	X	X	X	X	X	X	
Ventilator Parameters#†	X	X	X	X	X			X				
Arterial Blood Gases	A	A	A	A	A			A				
K+, HCO 3 , glucose	A	A	A	A	A			A				
Pneumothorax (y/n)*	X										X	
Use of rescue procedures (y/n)*											X	
Fluids (intake/output)	X	X	X	X	X	X	X	X				
Central Venous Pressure	A	A	A	A	A	A	A	A				
On-study meds: sedative, opioid, corticosteroid administration (y/n)	X	X	X	X	X			X				
SOFA Score (modified) B	X	X	X	X	X	X	X	X	X	X	X	
Manual Muscle Testing (with screening)								X	X	X	X	
Paralysis recall assessment**											X	
Plasma Collection	X	X	X									
Urine Collection	X	X	X									
Whole Blood collection for DNA/RNA	X		X									
Vital Status§											X	X

X=Required

A=When available

†= Data gathered at times indicated or until 48 hours UAB, whichever occurs first

\*\*=Collected once during study hospitalization

B=Records clinically available creatinine, platelets, bilirubin, SBP and vasopressor use

~=Data gathered on days 0-28 or until d/c from study hospital

#=Measure during reference period (0600-1000); other values may be obtained closest to 0800 on the specified calendar date

§=Also measure at 6 and 12 months as part of Long Term Outcome.

\*= Assessed for days 1-28 once on day 28 or discharge

## C ADVERSE EVENT REPORTING AND UNANTICIPATED PROBLEMS

As noted in section 11.2, investigators will report all adverse events that are serious and study drug or study procedure related to the CCC within 24 hours. The CCC will then notify the NHLBI and cIRB.

The Medical Monitor at the CCC will work collaboratively with the reporting investigator to determine if a serious adverse event has a reasonable possibility of having been caused by the study drug or procedure, as outlined in 21 CFR 312.32(a)(1)I, and below (Appendix C2). The Medical Monitor will also determine if the event is unexpected. An adverse is considered “unexpected” if it is not listed in the investigator brochure or the study protocol (21 CFR 312.32(a)). For this study, the cisatracurium (Nimbex®) package insert and the ACURASYS Study serve as the investigator brochure. If a determination is made that a serious adverse event has a reasonable possibility of having been caused by the drug, it will be classified as a suspected adverse reaction. If the suspected adverse reaction is unexpected, it will be classified as a serious unexpected suspected adverse reaction (SUSAR).

The CCC will report all unexpected and study related deaths, SAEs, and SUSARs to the DSMB, NHLBI, and cIRB within 7 days after receipt of the report from a clinical site. A written report will be sent to the NHLBI, DSMB and the cIRB within 15 calendar days. All unexpected and study related deaths and life threatening SUSARS will be reported to the FDA within 7 days; all other SUSARS will be reported to the FDA within 15 days. The DSMB will also review all adverse events and clinical outcomes during scheduled interim analyses, including frequency of additional neuromuscular blockade use in both study groups, for the first 48 hours. If the DSMB determines that the overall rate of adverse events is higher in the cisatracurium group than the control group the cIRB and the FDA will be notified within 15 days of this determination (via an IND safety report (21 CFR 312.32(c)(1)(i)(A))). The CCC will distribute the written summary of the DSMB’s periodic review of adverse events to the cIRB in accordance with NIH guidelines (<http://grants.nih.gov/grants/guide/notice-files/not99-107.html>).

